7.3. Study device

Fibro-Gide, a porcine, porous, resorbable and volume-stable collagen matrix, will be used for this investigation. It is a class III medical device according to the Medical Device Directive 93/42 EEC's definition: 1.1. long term implant, 1.2. implantable and rules 8 (resorbable) and 17 (animal origin). The material is weakly cross linked using EDC ((1-ethyl-3-3-dimethylaminopropyl) carbodiimide). CE certificate G7 1607 39446 073 for Geistlich Fibro-Gide® was issued on 12.08.2016 for the intended use of soft tissue augmentation in the oral cavity.

All matrices will be provided by Geistlich as a contribute to the project.

7.4. Post-operative procedures

Post-surgically, all patients will be given antibiotics for 6 days and were instructed to rinse their mouth with a 0.2% chlorhexidine solution, three times a day for 1 min. for 1 months.

Patients will be instructed to avoid brushing in the operated area until 2 weeks after surgery and instructed in mechanical tooth cleaning using a soft toothbrush.

All patients will be recall after 1, 2 and 4 weeks. They will be further recalled 3, 6 and 12 months after surgery for professional oral hygiene procedures and measurements.

7.5. Follow-up

Patients will be followed for 12 months after surgery.

At 7 ± 2 days post-surgery – general examination, photographic picture of the treated site questionnaire about post-operative pain.

At 14 ± 4 days post-surgery – suture removal, photographic pictures of the treated site

At 1 month ± 7 days post-surgery – general examination, photographic picture of the treated site

At 3 months ± 15 days post-surgery - general examination, photographic picture of the treated site, measurements of the following parameters: Gingival recession depth (REC in mm), Keratinized tissue width (KTW in mm), Gingival thickness (GT in mm), Pocket probing depth (PPD in mm), BoP, PI.

At 6 ± 1 months post-surgery - general examination, photographic picture of the treated site, evaluation of the aesthetic outcome, measurements of the following parameters: Gingival recession depth (REC in mm), Keratinized tissue width (KTW in mm), Gingival thickness (GT in mm), Pocket probing depth (PPD in mm), BoP, PI.

At 12 ± 2 months post-surgery - general examination, photographic picture of the treated site, evaluation of the aesthetic outcome, measurements of the following parameters: Gingival recession depth (REC in mm), Keratinized tissue width (KTW in mm), Gingival thickness (GT in mm), Pocket probing depth (PPD in mm), BoP, PI.

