2. FLOW-CHART

Evaluation	Screening phase	Study phase						End of study
	Screening	Surgery	Post treatment follow-up					
		Day 0	Day 7±2	Day 14±4	Day 30±7	Day 90±15	Day 180±30	Day 360±60
Demographic data	X							
Inclusion/Exclusion criteria	X							
Previous medical history	X							
Informed consent	X							
Clinical examination	X							
PPD, BoP, PI	X					X	X	X
REC, KTW, GT	X					X	X	X
Oral hygiene instructions	X	X		X				
Treatment								
Randomization		X						
Mucogingival surgery		X						
Use of Fibro-Gide		X						
Compliance			X	X	X	X	X	X
Suture removal				X				
Photography		X	X	X	X	X	X	X
Pain assessment (VAS)			X					

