The porcine-derived bio-resorbable collagen matrix (CM) (Fibro-Gide) is now prepared for placement on the interested areas: the width of the matrix must be reduced to 3-4 mm and the matrix has to adapt to the receiving tissues, when placed, a suture (6/00) must be used to hold it in position. Sling sutures (6/00) are performed to accomplish a precise adaptation of the buccal flap on the exposed root surfaces and to stabilize every single surgical papilla over the interdental connective tissue bed.

- Modified coronally advanced tunnel technique (MCAT)

Immediately before surgery, composite stops are placed at the contact points to prevent collapse of the future suspended sutures into the inter-proximal spaces.

After local anaesthesia, root planing of the exposed root surface is performed by means of hand instruments. Ethylenediaminetetraacetic (EDTA) is applied on the sites.

Subsequently, intra-sulcular incisions were placed and muco-periosteal flap separation are raised using sharp tunnel elevators. The muco-periosteal dissection is extended beyond the muco-gingival junction (MGJ) and under each papilla, to allow passive, tension-free mobilization in coronal direction. Muscle fibres and any remaining collagen bundles on the inner aspect of the flap alveolar mucosa are cut using Gracey curettes with extreme care in order to obtain a passive coronal positioning of the flap and the papilla and to avoid perforation of the flap.

The porcine-derived bio-resorbable collagen matrix (Fibro-Gide) is now prepared for placement on the interested areas: the width of the matrix must be reduced to 3-4 mm, then it can be inserted under the CAMT by starting at the deepest recession. Then, the site is rinsed with saline solution to remove any clot. The matrix has to be held in position using a suture (6/00).

Finally, the flap is positioned coronally to CEJ by means of suspended sutures (6/00) around the contact points.

At surgery, the duration of the full procedure will be evaluated (from anesthesia to suture).

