9.3. Responsibilities of the investigator(s)

The investigator(s) undertake(s) to perform the clinical trial in accordance with this clinical trial protocol, ICH /Good Clinical Practice and the applicable regulatory requirements.

The investigator is required to ensure compliance with all procedures required by the clinical trial protocol and with all study required procedures. The investigator agrees to provide all information requested in the Case Report Form (CRF) in an accurate and legible manner.

Furthermore, the investigator commits to give immediate notice of any Adverse Event and/or Serious Adverse Event (AE/SAE).

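### Section 7.5 and the flow-chart disagree on examinations at five post-operative visits, and nothing in the plan collects complications by technique

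*Combined protocol and SAP*

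**What the plan says.** **Section 7.5 (Follow-up).** The first visit reads "At 7 ± 2 days post-surgery – general examination, photographic picture of the treated site questionnaire about post-operative pain", and the third reads "At 1 month ± 7 days post-surgery – general examination, photographic picture of the treated site". A general examination is also listed at 3, 6 and 12 months. The second visit is the exception: "At 14 ± 4 days post-surgery – suture removal, photographic pictures of the treated site".

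**Section 2 (Flow-chart).** The row "Clinical examination" is marked at Screening and nowhere else. Photography is marked from Day 0 to Day 360. Compliance is marked at every post-operative visit. The periodontal measurements (PPD, BoP, PI, REC, KTW, GT) are marked at Screening and at Days 90, 180 and 360. There is no row for adverse events or complications.

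**Section 7.2 (Surgical procedures).** The tunnel description asks for care in cutting the muscle fibres, partly "to avoid perforation of the flap". The description of the coronally advanced flap has no corresponding remark.

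**Section 9.3 (Responsibilities of the investigator).** This is the only provision on adverse events: "the investigator commits to give immediate notice of any Adverse Event and/or Serious Adverse Event (AE/SAE". It names no visit, form or method of enquiry.

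**Sections 4.2 and 8.3.** The secondary outcomes cover root coverage, tissue dimensions, pain, drug intake, aesthetics and duration of surgery. Neither a complication outcome nor a safety analysis is listed.

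**The concern.** There are two linked problems.

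First, staff who work from the flow-chart and staff who work from section 7.5 would carry out different post-operative visits. On the flow-chart alone, no clinical examination follows surgery, and the first post-operative clinical measurements come at Day 90 ± 15.

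Second, the plan places a duty to report adverse events on the investigator but gives no procedure for finding them. The trial compares two operations, both using an implanted class III device (section 7.3), and the synopsis describes it as open label. What gets reported then depends on what each patient mentions and on what an unblinded investigator thinks worth notifying. Counts obtained that way need not be comparable between arms. If complete root coverage turns out similar, complications would be a natural basis for choosing between the techniques, and the trial would have no usable data on them. Some of this cannot be recovered afterwards: photographs will not show bleeding between visits.

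**Working it through.** **Step 1. Set the two schedules side by side.** The inputs are the visit list in section 7.5 and the clinical examination row of the flow-chart, taking the extracted table's column positions as correct.

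| Post-operative visit | General examination in 7.5 | Clinical examination in flow-chart | Agree? |
|---|---|---|---|
| Day 7 ± 2 | listed | not marked | no |
| Day 14 ± 4 | not listed | not marked | yes |
| Day 30 ± 7 (1 month) | listed | not marked | no |
| Day 90 ± 15 (3 months) | listed | not marked | no |
| Day 180 ± 30 (6 months) | listed | not marked | no |
| Day 360 ± 60 (12 months) | listed | not marked | no |

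The schedules disagree at 5 of 6 post-operative visits. At Day 14 they agree, because neither lists an examination.

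**Step 2. Check what is seen around Day 14.** The windows are Days 5–9 (Day 7 ± 2), Days 10–18 (Day 14 ± 4) and Days 23–37 (Day 30 ± 7). The longest gap between two visits is the latest day of the later one minus the earliest day of the earlier one.

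- Day 7 visit to Day 14 visit: 18 − 5 = 13 days.
- Day 14 visit to 1-month visit: 37 − 10 = 27 days.

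The patient therefore attends, has sutures removed and is photographed between Day 10 and Day 18. What is missing is a statement of which site assessment, if any, is recorded then.

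**Step 3. Search for any collection of complications.**

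| Place | Adverse events or complications collected? |
|---|---|
| Flow-chart rows | none; the compliance row is not defined |
| Visit contents in 7.5 | none |
| Outcomes in 4.1 and 4.2 | none |
| Analyses in 8.3 | none |
| Section 9.3 | duty of notice only, not tied to a visit |

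Flap perforation illustrates the gap. Section 7.2 names it for the tunnel arm, but no item records whether it occurred in either arm.

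**Step 4. What a per-arm count could show.** The plan enrols 18 patients per arm (section 8.1). For 0 events in n patients, the exact two-sided 95% upper limit is 1 − 0.025^(1/n). With n = 18, this is 1 − 0.025^(1/18) = 1 − 0.815 = 0.185, or about 18.5%. Even complete ascertainment with no events leaves a wide interval, so the outcome can only be descriptive. Incomplete ascertainment would leave still less.

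The documents state no figure of their own on this point, so there is none to reproduce.

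**The case against.** **The examination mismatch may be partly one of terms.** Section 7.5 speaks of a general examination and the flow-chart of a clinical one, and neither is defined. The flow-chart does mark site measurements at Days 90, 180 and 360. This softens the conflict but does not remove it. The flow-chart has no row for a general examination under any name, and at Day 7 and 1 month it shows no clinical assessment of the site beyond photographs.

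**Burden is already compared.** Pain, drug intake, duration of surgery and aesthetics, including a one-year keloid score, are outcomes by arm. That is true and useful, but none of them counts infection, dehiscence, matrix exposure or perforation.

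**The CRF may contain an adverse-event page.** It is not among the documents, so this cannot be excluded. The point is therefore limited to what the protocol specifies. It cannot be said that adverse events will go unrecorded at every visit.

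**A small trial cannot settle complication rates.** The 18.5% limit shows this. The objection stands against any inferential claim, but not against a descriptive count.

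**Stronger readings that the documents do not support.**

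- A reader might infer that the wound goes unexamined for up to 32 days (37 − 5, from the earliest Day 7 visit to the latest 1-month visit). That is only the interval between listings of a general examination. The patient is seen and photographed on Days 10–18, and the longest gap between attended visits in this period is 27 days.
- A reader might tie that interval to the antibiotic course, since "Post-surgically, all patients will be given antibiotics for 6 days". The course does not enter the visit arithmetic. Only a visit on Day 5, or on Day 6 depending on how the course is counted, could overlap it.
- A reader might infer that the trial will declare the techniques interchangeable if complete root coverage does not differ significantly. No section says so.

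**Conclusion.** The point holds as a reconciliation and data-collection matter, and should be fixed. The protocol text and the flow-chart disagree at five of six post-operative visits, and at Day 14 both leave the recorded site assessment unstated. Complications rest on a duty of notice alone, so the plan as written would not yield complication data comparable by technique.

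This rests on three assumptions: the flow-chart was extracted with its marks in the right columns, the compliance row does not cover adverse events (the document does not define it), and no unseen CRF page fills the gap. The primary outcome and its analysis are not affected. The documents do not show a period in which the wound goes unseen, and nothing here bears on the length of antibiotic treatment.

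**What to change.** 1. Reconcile the flow-chart with section 7.5 for the five visits at which they differ, using one defined term. State what site assessment, if any, is recorded at Day 14. Whether an examination belongs there is for the investigators.
2. Add one flow-chart row for adverse events and surgical complications, marked at surgery and at each existing post-operative visit. Support it with a fixed yes/no checklist: flap perforation at surgery; infection, dehiscence, matrix exposure and bleeding afterwards. Ask every item in the same way in both arms. This matters most for perforation, which section 7.2 raises for one arm only.
3. Add to section 4.2 the number of patients per arm with at least one complication, and to section 8.3 its report as a descriptive outcome with an exact 95% confidence interval and no claim of equivalence.

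The cost is one CRF page, one flow-chart row, a line each in 4.2 and 8.3, and a few minutes per visit. No visit or procedure is added. The change concerns what is recorded, and takes no position on how any complication is managed.

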7.6. Investigator training

Five subjects not involved in the study, each showing a pair of single-rooted contra-lateral teeth with recessions $>$ of 2 mm on the mid-buccal aspect of each tooth, will be used to calibrate the examiner. The examiner will evaluate the subjects on two occasions 24 h apart. Calibration will be accepted if 90% of the recordings could be reproduced within a difference ≤ 0.5 mm (Aroca 2010).

8. STATISTICAL CONSIDERATIONS

8.1. Sample size calculation

The range of mean root coverage percentage of the two mucogingival techniques which can be found in literature varies between 85% and 95%. While the value of variability (SD) obtained in previous articles is 10%. On the basis of these settings, the sample dimension has been calculated using $\alpha = 0.05$ and the power (1- β) of 80%. The minimal significant value considered is 10%.

So, the needed number of patients to be enrolled in this study is 17 for the test group MCAF + Fibro-Gide and 17 for the MCAT + Fibro-Gide. However, the number of patients will be increased of 1 patient for each arm considering the possibility of dropout, so the required number will be 18 for each group.

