4.1. Primary outcome

- percentage (%) of complete root coverage (CRC) at 12 months

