4.2. Secondary outcomes

- percentage of root coverage (RC %) at 3, 6 and 12 months
- keratinized tissue width (KTW) at 3, 6 and 12 months
- gingival thickness (GT) at 3, 6 and 12 months
- post-surgical pain (PP),
- amount of drug intake after surgery
- patient perception of aesthetics at 6 and 12 months
- color match (blending), contour (correct outline of the gingival margin at adjacent teeth), contiguity (evaluated based on the visible confluence between the treated area and the adjacent soft tissues), degree of keloid formation scored at the 1-year post-surgical evaluation will be measured by an expert periodontist.
- duration of surgery (from anesthesia to last suture).

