8.2. Null hypothesis

H0: No statistically significant differences are observed with respect to the clinical parameters CRC, at 12 months between the two treatment modalities (i.e., MCAF + CM or MCAT technique with CM).

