8.3. Statistical Methods

Statistical analysis will be performed using commercially available software (STATA) or R environment (www.r-project.org). Both patient- and tooth-level analysis will be performed for each parameter. Therefore, mean values and standard deviations (SD), as well other descriptive statistics, for the clinical variables will be calculated for each patient per treatment.

A mixed model will be built to take into account the variability due to patient and tooth factors differentially.

Accordingly, the significance of the difference within each group and between groups before and after treatment will be evaluated with the paired samples t-test or two independent samples t-test, as appropriated, regarding all numerical data (REC, KTW, GT, PPD, percentage of root coverage and VAS scale).

Fisher's exact test will be applied for categorical data (frequency of complete root coverage).

P-values will be computed by means of permutation methods to avoid any distributional assumptions or asymptotical approximation. Differences will be considered statistically significant when the p-value was <0.05 .

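### The 17 per arm and 80% power in section 8.1 are for mean root coverage %, a secondary outcome; the plan gives no power for the primary outcome, complete root coverage

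*Combined protocol and SAP*

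**What the plan says.** - **Primary outcome (section 4.1):** "percentage (%) of complete root coverage (CRC) at 12 months". The null hypothesis in section 8.2 concerns the same outcome: "No statistically significant differences are observed with respect to the clinical parameters CRC, at 12 months between the two treatment modalities". The synopsis repeats it.
- **Secondary outcomes (section 4.2)** include "percentage of root coverage (RC %) at 3, 6 and 12 months". The glossary also defines CRC and RC % separately.
- **Sample size (section 8.1):** "The range of mean root coverage percentage of the two mucogingival techniques which can be found in literature varies between 85% and 95" per cent. It adds an SD of 10%, a smallest difference of interest of 10%, alpha 0.05 and power 80%. The result is 17 per arm, raised to 18 for dropout.
- **Analysis (section 8.3):** t-tests are used "regarding all numerical data (REC, KTW, GT, PPD, percentage of root coverage and VAS scale"), and Fisher's "exact test will be applied for categorical data (frequency of complete root coverage"). It also says "Both patient- and tooth-level analysis will be performed for each parameter", plans a mixed model, and states "P-values will be computed by means of permutation methods".
- **Synopsis, statistical considerations:** the 17 per arm comes directly after the CRC hypothesis, without saying which variable it was calculated for.

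**The concern.** A power statement covers only the outcome, effect and test from which it was calculated. Here the calculation concerns the mean of a continuous variable, while the primary test compares the frequency of a categorical one. The two outcomes are related, but neither determines the other: a mean coverage of 85% or 95% does not fix the share of patients or teeth that reach full coverage.

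A reader who meets the sample size straight after the CRC hypothesis in the synopsis, or the 80% in 8.1, will take both as support for the primary test. If CRC is then not significantly different, nothing in the plan says how large a difference the trial was able to detect.

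**Working it through.** **1. Reproduce 8.1.** Inputs from section 8.1: difference 10, SD 10 (standardised difference 10/10 = 1), alpha 0.05, power 80%. Sidedness is not stated; two-sided is inferred because it matches.

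- Normal approximation: n = 2 × (1.960 + 0.842)² / 1² = 15.7, so 16 per arm.
- Noncentral t at 17 per arm: noncentrality 1 × √(17/2) = 2.915, 32 df, critical value 2.037, power 80.7%.
- At 16 per arm power is 78.1%; at 18 it is 83.0%.

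So 17 is the smallest size that reaches 80% for mean RC %. The figure is correct for that outcome.

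**2. Look for a CRC counterpart.** Section 8.1, the synopsis and the rest of the protocol give no CRC rate, CRC difference or CRC power. Every CRC rate below is therefore an assumption.

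**3. What 17 per arm gives if CRC is one yes/no result per patient.** Power = Σ Bin(x; n, p₁) × Bin(y; n, p₂) over all tables (x, y) with two-sided Fisher p < 0.05, by full enumeration.

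| Assumed CRC rates | Power, 17 per arm | Power, 18 per arm |
|---|---|---|
| 10% v 59% | 81.0% | 84.6% |
| 20% v 71% | 81.1% | 85.2% |
| 20% v 50% | 31.9% | 35.9% |

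A permutation p-value based on the absolute difference in proportions equals Fisher's two-sided p in every table at both sizes, so the permutation clause in 8.3 leaves these figures unchanged.

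**4. Difference needed for 80% power at 17 per arm.** It depends on the lower rate:

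| Lower rate | Difference needed (points) |
|---|---|
| 0% | 36.4 |
| 5% | 44.2 |
| 10% to 30% | 48.5 to 50.5 |
| 50% | 44.7 |
| 55% | 41.8 |
| 60% | 38.7 |
| 63% | 36.8 |

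At 18 per arm the 10% to 30% row becomes 46.3 to 48.3.

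**5. Do 8.1's inputs settle the CRC rates?** Suppose RC % and CRC share the patient as unit and RC % cannot exceed 100. The one-sided Chebyshev bound on the share of patients at 100% is SD² / (SD² + (100 − mean)²):

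- mean 85: 100 / (100 + 225) = 30.8%;
- mean 95: 100 / (100 + 25) = 80%.

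These are upper limits only. The pairs 20% v 50% and 20% v 71% both lie within them, and each admits a distribution on 0 to 100 with means 85 and 95 and SD 10. The same planning inputs are therefore compatible with 31.9% power and with 81.1% power for CRC.

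**6. Precision of a null result.** Illustration: 10/17 in both arms (58.8%). Wilson limits are 36.0% and 78.4%. Newcombe interval for the difference: ±√(22.8² + 19.6²) = ±30.1 points.

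**The case against.** **The unit of CRC is open, so the Fisher figures may not apply.** This stands. Section 4.1 speaks of a percentage, each patient has at least two recessions (section 6.1), and 8.3 plans both patient-level and tooth-level analyses. CRC could be one yes/no result per patient, one per tooth, or the percentage of a patient's teeth with complete coverage. The figures in steps 3 to 5 hold only for the first. The other two cannot be calculated from the plan: it gives no expected number of teeth per patient, no within-patient correlation and no SD for a per-patient percentage. This limits the illustration, not the mismatch.

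**A single detectable difference would be simpler.** A reader might infer that 17 per arm reaches 80% power only for CRC differences of about 45 to 50 points. That is false without a condition on the lower rate: step 4 shows 36 to 44 points when the lower rate is 5% or less, and 37 to 42 points when it is 55% to 63%. The 44.7 points at a lower rate of 50% also lies outside the 30.8% limit in step 5.

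**The plan does not claim equivalence.** Also correct. Nothing in the protocol says that a non-significant result will be read as showing the techniques alike. But H0 is worded as no significant difference being observed, which any non-significant result satisfies, so the wording invites that reading. This is a secondary point.

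**Conclusion.** The mismatch is established from the text and from the exact reproduction of 17 per arm. The only stated power belongs to mean RC %, a secondary outcome, and does not apply to the primary comparison of CRC.

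Two stronger conclusions are tempting and are not supported:

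- **That the trial is underpowered for CRC.** The documents give no CRC rates, and 8.1's inputs fit both 31.9% and 81.1% power under one yes/no result per patient. Power is undetermined.
- **That power is about 5%.** That figure comes from carrying 8.1's 10% over to CRC (for example 4.9% for 50% v 60% and 4.4% for 85% v 95% at 17 per arm). Section 8.1 states its 10% for mean root coverage, not for CRC.

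The CRC figures rest on assumed rates, one binary result per patient and a two-sided 5% level. The mismatch itself rests on none of these.

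**What to change.** **1. Sections 8.1 and synopsis.** State that 17 per arm gives 80% power for mean RC % only, and that this is a secondary outcome.

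**2. Sections 8.1, 8.3 and synopsis.** Name the unit of the primary CRC analysis (one yes/no result per patient, one per tooth, or the per-patient percentage of teeth with complete coverage) and state what 17 per arm gives for it. If it is one result per patient, conditional wording such as this would do:

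> With one CRC result per patient and Fisher's exact test, 17 per arm gives about 81% power for assumed rates of 10% v 59% or 20% v 71%, and about 32% for 20% v 50%. For lower-arm rates of 10-30%, 80% power needs a difference of about 48-51 points.

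If the unit is the tooth, give the assumed teeth per patient and within-patient correlation. If it is a per-patient percentage, give its SD. The figures above do not carry over to either.

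**3. Section 8.3, secondary.** Report the CRC difference with its 95% confidence interval, and state that a non-significant result will not be read as showing that the techniques perform alike.

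**Cost.** Wording only: no extra patients and no change of primary outcome. The stated support for the primary comparison becomes less favourable, and the new wording discloses the gap without showing that 17 per arm is enough for CRC.
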